3.5 Acute Treatment

3.5.1 Endovascular Therapy: In patients randomized to endovascular therapy, the goal for femoral artery puncture will be within 45 minutes of randomization; femoral artery puncture must occur within 90 minutes of the completion of the qualifying imaging. Patients will be treated with thrombectomy devices (stent-retrievers) and/or suction thrombectomy systems currently cleared by the FDA for thrombus removal in patients experiencing an acute stroke within 8 hours of symptom onset following the published instructions for use for these devices. These devices will be used up to 16 hours following symptom onset in DEFUSE 3 based on an FDA IDE. The devices which will be used are the Trevo Retriever, the Solitaire Revascularization Device, Covidien MindFrame Capture Revascularization Device and the Penumbra thrombectomy system.

Standard medical therapy, based on current AHA guidelines, will also be provided for all patients. Individual investigators may use any of these devices or any combination of these devices to remove thrombus from the ICA, MCA M1 segment or, if needed, from M2 segments of the intracranial circulation. These are all approved anatomic locations for these devices. The use of thrombectomy devices should be performed in accordance with the indications for use. If there is a severe stenosis of the common carotid artery or the proximal internal carotid artery, investigators may also use other FDA devices approved for angioplasty or FDA devices approved for stenting of the carotid artery as deemed appropriate. The use of adjuvant intra-arterial (IA) thrombolytic medication is not currently approved by the FDA for stroke treatment and cannot be used in DEFUSE 3.

Sites will use local protocols for femoral access, sedation, heparin infusion, monitoring, etc. Sites will perform a cervical injection of the involved carotid circulation as a baseline

angiogram. At the conclusion of the procedure, a post-treatment angiogram as a cervical injection of the involved carotid circulation will also be obtained. Imaging will cover the full region of the normal circulation in AP and lateral projections at 2-3 films per second through the entire venous phase. All brain imaging from stroke onset through hospital discharge, including the baseline MRI and CT, as well as angiographic images obtained for the diagnostic and therapeutic portions of the procedure, will be transmitted to the core lab.

3.5.2 Medical Therapy: Patients randomized to medical therapy will receive standard medical therapy based on current AHA guidelines. Based on the time window for DEFUSE 3, it is anticipated that very few of the patients enrolled in DEFUSE 3 will have received iv tPA prior to randomization (“tPA failures”). For these patients, the sites’ post-tPA protocol will be followed. Non-tPA treated patients randomized to medical therapy will be treated with aspirin, 325 mg on Day 1, and 81-325 mg/day (investigator’s preference) on day 2-5, unless an indication for early anticoagulation is present (as determined by the patient’s attending physician). All patients will receive standard DVT prevention therapy. Intravenous anticoagulants are prohibited (unless a clear indication for early anticoagulation is documented); dual antiplatelet therapy is prohibited unless carotid stenting was performed during the endovascular procedure or a clear indication for dual antiplatelet therapy is documented. Subsequent antithrombotic therapy will be determined by the patient’s attending physician.

3.6 Clinical and Imaging Evaluations

Follow-up (imaging and clinical): Randomized patients will be followed clinically for 90 days and will have an MRI/MRA/MR perfusion at 24 hours (range 18-30 hours) to assess infarct volume, recanalization, hemorrhage and reperfusion (**Table 1 below**).

Table 1 Schedule of Events

	Screening	Enrollment	Baseline / Randomization	Endovascular Procedure	24 hours (+/-6 hrs)	Hospital Discharge	Day 30 (+/- 7 days)	Day 90 (+/- 14 days)
Screen Failure Log	X							
Informed Consent		X						
Subject Enrollment		X						
Inclusion and Exclusion Criteria			X					
MRI or CTP			X		X**			
Randomization			X					
Medical History			X					
Vital Signs			X					
NIH Stroke Scale			X		X	X	X	X
Modified Rankin Scale			X*			X	X	X
Baseline ASPECTS Score			X					
Baseline Labs*			X					
Endovascular Therapy				X				
24 Hour Labs					X			
Hospital Discharge						X		
Adverse Event Assessment				X	X	X	X	X
NeuroQOL								X

*Laboratory Evaluation includes CBC with Platelets, Creatinine, Glucose, INR, activated PTT, and Pregnancy test (if applicable). At 24 hour follow-up only creatinine is required. † Historical mRS at baseline, mRS/NIHSS to be performed by an NIHSS/mRS certified member of the research team who is blinded to treatment allocation at 30 and 90 days. ** Patients will preferably undergo an MRI with MRA AND MR Perfusion at 24 hours; if an MR cannot be performed, a CT with CTA AND CTP can be substituted. For patients who are consented but not randomized, the schedule of events is limited to a summary of stroke therapies received within 24-hrs of stroke onset.

3.6.1 Assessments and follow-up visits

Baseline visit: All items in Table 1 above listed under “baseline” are to be performed prior to randomization. The MRI or CT scan should be performed with the DEFUSE 3 (baseline) protocol, which will be installed at all study sites. In addition, the inclusion/exclusion page of the case report form must be completed to determine if the patient meets the eligibility requirements for the study. If the patient is eligible and the consent form is signed by the patient or authorized representative, then the randomization procedure should occur immediately.

24 hour visit (+/- 6 hours): The items listed for this visit in Table 1 should be performed between 18 and 30 hours from the time of randomization. The only laboratory value required at the 24 hour visit is a serum creatinine. If possible, the 24 hour follow-up imaging study should be performed with multimodal MRI, rather than CT perfusion. The MRI or CT scan performed at this time should be performed with the DEFUSE 3 protocol.

Discharge visit: The items listed for this visit in Table 1 should be performed on the day of hospital discharge

30 and 90 day visits: The items listed for this visit in Table 1 should be performed on Day 30 (+/- 7) days and Day 90 (+/- 14) days. The mRS score must be performed by an mRS certified investigator who is blinded to treatment allocation at both the 30 and 90 day visits. If an in person visit is not possible, then the mRS should be performed by phone by an mRS certified investigator who is blinded to treatment allocation. If an in person visit is not possible, then the NIHSS score will be marked “not available” in the case report form.

Neurological worsening: If clinical worsening (defined as a ≥ 4 point increase on the NIHSS score) occurs prior to discharge, a CT scan or MRI should be obtained as soon as possible. Neurological worsening is a reportable adverse event.

3.6.2 Sources of Materials

Information on the clinical status of patients will be obtained from the patient’s medical record. Study coordinators at the site will complete the DEFUSE 3 case report forms to collect basic demographic and medical information about the patients. Data will subsequently be entered into the StrokeNet’s WebDCU electronic data capture system. Imaging data will be electronically transmitted to the coordinating center at Stanford via RAPID (all patient identifiers are removed by the software prior to exporting the data outside of the site’s firewall). All study sites will complete a stroke screening log that documents all patients treated in the cath lab beyond 6 hours at their center, and reason for exclusion of patients not enrolled, in the StrokeNet’s WebDCU electronic data capture system. Serious adverse events (SAEs) will be reported within 24 hours of the event in the StrokeNet’s WebDCU electronic data capture system. The data collection process will include patient demographics, medical history, vital signs, laboratory assessments, NIHSS and mRS scores, and results of diagnostic studies performed to clarify stroke etiology.

3.7. Site Approval and Monitoring Plan

Site approval: Individual sites approved for participation in the study will be high-volume sites. Selected sites will have access to emergent CT perfusion and/or MR imaging 24/7. Prior to activating a site, we will verify that RAPID is functional at the site. Together with the

site's CT and/or MR technologists, we will install the DEFUSE 3 scan protocol on the local scanners and perform a dummy-run to assess image quality and train the technologists in software handling and data sending. A site will be activated for enrollment after test cases processed with RAPID have ensured good quality maps.

Monitoring for imaging quality: The Imaging Core Lab will monitor image quality throughout the study. If significant inadequacies or protocol errors are noted at a site, enrollment will be halted. Enrollment will resume after all imaging problems have been resolved and repeat dummy runs have been obtained that demonstrate adequate image quality.

Table 2. Example Imaging Sequences for DEFUSE 3 scans

Sequence	Scan Parameters (3T)	Time
MRI		6 min
Localizer	128X256; 28 FOV;5/5mm, GRE	24 sec
Calibration		5 sec
DWI	128x128, 24 FOV, 5/0mm, 30 slices, 1 NEX, R=2; b=0 and 1000 s/mm ² over 3 axes, TE/TR=min/7000ms.	25 sec
GRE	256x192; 24 FOV; 5/0 mm, 30 slices, TE/TR= 25/800ms, flip 20, interleaved EPI, 16 shots	27 sec
MRA intracranial	256x192, 1 mm; 4 slabs, 26 phase-encodes; 6 overlap, 22 FOV, 0.8 rFOV, fractional echo, ZIPx2, ZIPx512, minTE, flowcomp, TR=18ms, flip=18, inferior->superior rampulse, R=2; 19 MIPS	143 sec
PWI	128x128; 24 FOV; 5/0 mm, 17 slices, TE/TR=35ms/1800ms, R=2 using 0.1mmol/kg Gadolinium @ 4ml/sec.	108 sec
CT (example below for GE VCT; comparable protocols will be used for other scanner models)		5-6 min
Non-con head	2.5 – 5mm, 40 slices, 120-140kV, 265-290mA	120-180 sec
CTA	0.625mm, 0.984:1/39.37cm, 120kV, 550mA , inject and observe for 15 sec until contrast concentration in ascending aorta reaches 80HU (smart prep) then the CT gantry moves along with the bolus of the contrast material from the aortic arch up to the apex of the brain in 5sec.	90 sec
CTP	22 FOV, 40mm, 8x5mm, 1.8sec time interval, 45 cycles, 80kV, 125mA; 2 runs	90 sec

Monitoring for bias: A detailed site-monitoring plan has been developed to detect bias. This plan will protect the study from enrollment, randomization, and treatment bias. The first component involves monitoring the percentage of each site's endovascular volume (within 6-16 hrs) that is enrolled in DEFUSE 3. Sites will report their volume of endovascular stroke procedures (within 6-16 hrs) each month on a screening log. If a DEFUSE 3 eligible patient is treated with endovascular therapy outside the DEFUSE 3 study, an explanation will be required detailing why the patient was not enrolled. The second component of the plan involves tracking of patients who are consented but not randomized. These patients will require an entry in the WebDCU with an explanation why the patient was not randomized as well as documentation whether endovascular therapy was performed outside of the study. A third component involves monitoring of crossover after randomization. The Executive Committee will review the data described above for each site every 6 months. If evidence of enrollment bias is suspected, it will be investigated. If confirmed, the site will be placed on probation. If additional incidents of

suspected bias are confirmed, the site will be withdrawn. Routine monitoring of the clinical sites for source to database verification will be performed by the StrokeNet Data Management Center.

3.8. Sample Size, Adaptive Design and Statistical Analysis

DEFUSE 3 will feature a novel adaptive trial design that will allow the study to focus on a subpopulation if interim or final analyses indicate futility in the overall population.⁵⁹ The adaptive design was developed specifically for DEFUSE 3. It is based on closed testing theory and the group sequential methods for the Generalized Likelihood Ratio (GLR) statistic developed by Lai and Shih.⁶⁰ The adaptive design was chosen because there is strong preliminary data that suggests that the effect of endovascular treatment is modified by two baseline variables: core lesion size and time-to-treatment. The way the adaptive design takes advantage of these biological assumptions (when they are true) is by reallocation of future accrual to the subgroup with the best prospects for showing efficacy. Specifically, if a subgroup is chosen at an interim analysis, subsequent enrollment is limited to patients in that subgroup. As a result, this subgroup will become larger than it would have been in the absence of the adaptive design. The criterion for deciding which subgroup has the best chance of showing a benefit from endovascular therapy combines both the estimated size of the effect in the subgroup and the sample size of the subgroup. The GLR statistic (Kullback-Leibler criterion) is used to identify this subgroup because it optimally balances those two criteria. It selects the subgroup that has the best chance of showing an effect because it has an apparently large effect and is also of substantial size (note there are 5 subgroups of increasingly larger size, **figure 3**). The adaptive design employs two biologically-based assumptions to limit the inflation of sample size; a monotonicity/contiguity assumption and an a priori assumption that the effect is largest in the patients with the smallest DWI lesions and the shortest time to randomization (cell C₁₁ in **figure 3**). The boundaries of the categories (cells) will be determined just prior to the 1st interim analysis based on the distribution of patients across these two dimensions (lesion volume and time-to-treatment).

Primary analysis: The primary endpoint is the distribution of scores on the modified Rankin Scale (mRS) at day 90. We will test the null hypothesis at the interim and final analysis using a normal approximation of the Wilcoxon-Mann-Whitney test (the generalized likelihood ratio [GLR] test). The primary analysis will be intention to treat, adjusted for design and not adjusted for covariates.

For each analysis, an efficacy bound will be set to control the overall (one-sided) Type I error rate at 2.5%. At each interim analysis a futility bound will be set to decide if the study should continue recruitment in the overall group, shift accrual and testing to a subgroup, or stop in its entirety. The futility boundary adapts when a subgroup is selected to the fact that the maximum analyzed sample size is a random variable that is no larger than the fixed maximum number of patients randomized (n=476). Because subgroup selection reduces the

		Time (hrs)	
		<10	10-16
Core lesion volume (ml)	≤20	C ₁₁	C ₂₁
	21-50	C ₁₂	C ₂₂
	51-70	C ₁₃	C ₂₃

Figure 3. The cohort is stratified according to core lesion volume and time to randomization. Exact boundaries of the stratification will be determined based on the distribution of patients just prior to the first interim analysis. Depending on the results of the 1st interim analysis, subsequent enrollment will continue in all 6 cells or will be limited to one of 5 sub-groups (C₁₁, C₁₁₊₂₁, C₁₁₊₂₁₊₁₂, C₁₁₊₂₁₊₁₂₊₂₂, or C₁₁₊₂₁₊₁₂₊₂₂₊₁₃).

maximum number of patients available for analysis at completion of the study, this method effectively allows an easier futility stop after subgroup selection. This setup replaces conditional power analyses with an automatic and more powerful adjustment of boundaries.

First interim analysis (n=200 randomized and completed 90 day follow-up): The null hypothesis is tested in the entire patient population:

1. If neither efficacy nor futility bound is crossed, the trial continues enrollment to the 2nd interim analysis.
2. If the efficacy bound is crossed, the trial stops and efficacy is declared in the overall population.
3. If the futility bound is crossed, the optimal subgroup is selected based on the Kullback-Leibler criterion and the null is tested in that subgroup. The futility bound is relaxed as described above, based on the expected maximum number of patients in the trial at completion (ie 476 minus the number of patients already enrolled in cells that will no longer be open for enrollment).
 - 3.1. If neither bound is crossed, the trial will continue with enrollment limited to the selected subgroup
 - 3.2. If the efficacy bound is crossed, the trial stops and efficacy is declared in the selected subgroup
 - 3.3. If the futility bound is crossed, the trial stops for futility.

Second interim analysis (n=340 randomized and completed 90 day follow-up): If, after the first interim analysis, the study proceeds with enrollment in the overall population (option 1 above), the testing at the 2nd interim analysis is identical to the first interim. If enrollment is limited to a selected subgroup (option 3.1), the null is tested in that subgroup:

1. If neither bound is crossed, the trial continues to the final analysis with enrollment of 136 additional patients limited to the selected subgroup
2. If the efficacy bound is crossed, the trial stops and efficacy is declared in the selected subgroup
3. If the futility bound is crossed, the trial stops for futility.

Final analysis (n=476 randomized and completed 90 day follow-up): If, after the second interim analysis, the study proceeds with enrollment in the overall population, the null is tested in the overall population:

1. If the efficacy bound is crossed, endovascular therapy is declared efficacious in the overall population.
2. If the efficacy bound is not crossed, the optimal subgroup is selected and the null is tested in that group:
 - 2.1. If the efficacy bound is crossed, endovascular therapy is declared efficacious in that subgroup
 - 2.2. If the efficacy bound is not crossed, endovascular therapy will be declared of no benefit.

If enrollment after one of the interim analyses is limited to a selected subgroup, the null will be tested in that subgroup only and efficacy or lack thereof will be declared as per options 2.1 and 2.2 above.

Power and sample size considerations: The projected overall effect of endovascular therapy is based on 1) the observed 90-day modified Rankin Scale outcomes in DEFUSE 2 of target mismatch patients treated >6hrs after symptom onset and 2) the assumption that early reperfusion will be achieved in 75% of the endovascular arm vs. 20% of the medical therapy arm.^{20, 21, 61} Using these data, we projected the distributions on the mRS at 90 days in the endovascular and control arms of DEFUSE 3:

	mRS at day 90							Total
	0	1	2	3	4	5	6	
Endovascular group	18.0%	11.5%	19.6%	11.5%	16.4%	11.5%	11.5%	100%
Medical group	9.7%	7.9%	15.0%	17.7%	14.4%	17.7%	17.7%	100%

This distribution corresponds to a standardized effect of 0.36 for the primary analysis. Based on these data, the fixed sample size for a non-adaptive design requires a total of 376 patients (188/arm) to have 90% power at an alpha of 5% (Wilcoxon-Mann-Whitney test); 100 additional patients are added for the adaptive design to reach a maximum sample size of 476 for DEFUSE 3.

We ran simulations (n=5000) to compare the performance of a traditional fixed sample-size design (fixed n=476) to the adaptive design (max n=476) under various scenarios (see **Table 3**, below). For the simulations the effect size is expressed as a standardized effect, where a standardized effect of 0.3 corresponds to a conservative projected effect of endovascular therapy (anticipated effect 0.36; see above).

Imaging outcomes: We hypothesize that endovascular treatment improves radiological outcomes in stroke patients with favorable clinical and imaging characteristics. DEFUSE 2 demonstrated a substantial reduction in infarct growth among Target mismatch patients treated in the 6-12 hour time-window who achieved early reperfusion: median growth 0.5 ml (IQR: -2 – 10) with reperfusion (n=23) vs. 39 ml (IQR: 18-121) without reperfusion (n=13), p<0.001. These data have been extrapolated to DEFUSE 3 using the same assumptions described above; anticipated an early reperfusion rate of 75% in the endovascular arm vs. 20% in the medical arm. This yields a sample size of 42 per group for 90% power. Therefore, DEFUSE 3 is highly powered to demonstrate differences in lesion growth. Infarct volumes, ischemic lesion growth, and reperfusion rates at 24 hours will be compared between groups with the Mann-Whitney U test. The 24 hour endpoint is based on data demonstrating that assessment of infarct volume at 24 hours captures the effect of reperfusion therapies on infarct growth and predicts outcomes similarly to day 90 infarct volumes.^{29, 62} RAPID-assessed ischemic core volume at baseline will be correlated with 24h infarct volume (DWI volume) in subjects who achieve reperfusion without PH1 or PH2 intracranial hemorrhage. Pearson's correlation coefficient will be calculated and the median absolute error (ml) will be reported. Similarly, correlation of the baseline Tmax >6 volume and the 24h infarct volume in patients without PH1 or PH2 intracranial hemorrhage who have <10% reperfusion will be performed. Correlation of RAPID predicted infarct volume (coregistered baseline ischemic core and 24h Tmax >6 volume) with the actual 24h infarct volume will also be performed.

Scenario	Standardized effect in cells							Average standard effect	Adaptive Design		Fixed Design	
	C11	C12	C21	C22	C31	C32	Average No. randomized		Power	Number randomized	Power	
#0	0	0	0	0	0	0	0	361	2.2%	476	2.5%	
#1	0.3	0.3	0.3	0.3	0.3	0.3	0.3	354	80%	476	89%	
#2	0.5	0.4	0.3	0	0	0	0.2	400	86%	476	55%	
#3	0.5	0.5	0	0	0	0	0.17	403	87%	476	41%	

Table 3. Under the null (Scenario #0), the adaptive design controls the total Type 1 error below 2.5%, stops early for futility 63% of the time, and the average number of randomizations is 361. If the effect is uniform across cells (scenario #1), the fixed-sample design is optimal, but the adaptive design results in only a small loss of power (from 89 to 80%). The adaptive design performs much better (higher power and smaller expected sample size) than the fixed sample, conventional trial when the effect size distribution across the subgroups is in accord with the biological assumptions (scenarios #2 and 3). If the effect is concentrated in two cells with small core volumes (scenario #3), the adaptive design maintains power (87%) while the conventional design collapses (41% power). The adaptive design also performs well compared to a non-adaptive, fixed sample that includes efficient multiple comparisons-adjusted testing for effect in subgroups at the end of the study. (see Lai et al⁵⁹)

Secondary analysis: Our secondary endpoint is the proportion of patients with mRS 0-2 at day 90 (indicating functional independence). The difference in the proportions of patients with mRS 0-2 between treatment arms will be assessed using logistic regression.

Subgroup analyses: Subgroup analyses of the effect of endovascular therapy on the primary and secondary endpoints will be performed. Subgroups will be defined based on the stratification variables, key demographic factors (such as race and ethnicity), tPA vs. no tPA, CTP vs. MRI selection, and witnessed vs. unwitnessed symptom onset, wake-up vs non-wake-up stroke, and TIC1 0-2a vs. TIC1 2b/3 results in cath lab.

Missing data/lost to follow-up (LTFU):

All effort is put forth to ensure near complete follow-up, in particular with the assessment of the primary outcome (mRS at 90 days), death (mRS=6), and stroke recurrence. If the primary outcome (mRS at 90 days) cannot be assessed in the clinic, it will instead be obtained by phone using a structured interview. If the subject’s mRS cannot be obtained in clinic or by phone within the window of 60 to 120 days from randomization, then for primary analyses the day 30 mRS score will be used as the primary outcome (ie day 30 mRS carried forward). If neither the 30-day nor the 90-day mRS is available, then the mRS will be imputed. We do not expect this to alter the main study results given our estimated very low LTFU rate (<2%).

DEFUSE 3 Timetable

Year 1	Year 2	Year 3	Year 4	Year 5
Install RAPID at all sites Begin enrollment (anticipated to begin mid-year)	Pt enrollment continues for a total of 4 yrs	1st interim analysis Potential modification of enrollment criteria based on adaptive design	2nd interim analysis Potential modification of enrollment criteria based on adaptive design	Finish enrollment Data Analyses Publication of results

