This proposed plan supersedes the prior SAP. No further interim analyses for adaptation will be conducted, and Sections 9.2-9.4 of the prior SAP are now deleted. Other changes include: Subgroup analysis related to time from symptom onset to randomization and baseline core volume (Section 12.2 of the prior SAP) define subgroups based on medians, rather than "cutpoint from adaptive design". An additional pre-specified exploratory analysis has been included that compares the primary and secondary efficacy and safety endpoints in DAWN-eligible vs DAWN-ineligible patients (see section 11.1). The remainder of the SAP will be followed as pre-specified prior to this revision.

This document provides the details of the statistical analyses planned for the DEFUSE 3 Trial, including the original interim analyses for efficacy, futility, and subgroup selection, and the revision to reflect the early interim analysis for overwhelming efficacy. In addition, it discusses

the statistical issues relevant to these analyses (e.g., sample data to be used, imputation of missing data, adjustments for multiplicity, etc.).

The NDMC generates DSMB Reports semiannually. Each semiannual report provides cumulative summary statistics on enrollment; subject status in the study (e.g., number completed 30 and 90 day assessments); baseline characteristics; protocol violations; safety data, including AEs and SAEs by AE code and relatedness to the study intervention; and data management/quality information (e.g., timeliness and completeness of data entry by the clinical centers via the StrokeNet WebDCU™ Website; number of DCRs generated and resolved). These statistics are reported by treatment group.

3. Study Objectives

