9.5. Reporting of primary results

The results of the study will be primarily expressed as whether or not an efficacy boundary was crossed at ~~either one of the two interim analyses or at the final analysis. The efficacy boundary is set, a priori, to guarantee less than a 2.5% one-sided error rate.~~ Crossing of the efficacy boundary will be considered evidence that endovascular therapy is beneficial, based on lower day-90 mRS scores in the endovascular group compared to controls.

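### Protocol 3.8 words a missed final efficacy bound as a finding of no benefit, which a superiority test cannot show

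*Protocol*

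**What the plan says.** Protocol 3.8 fixes the error rate first: "For each analysis, an efficacy bound will be set to control the overall (one-sided) Type I error rate at 2.5"%. It then lists what follows from each result.

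- **Interim analyses.** A miss of the efficacy bound leads to continued enrollment, to selection of a subgroup, or to a stop: "If the futility bound is crossed, the trial stops for futility".
- **Final analysis, enrollment still overall.** A miss in the overall population has a second step: "If the efficacy bound is not crossed, the optimal subgroup is selected and the null is tested in that group". If the subgroup crosses, efficacy is declared in that subgroup (option 2.1). If it does not, option 2.2 applies: "If the efficacy bound is not crossed, endovascular therapy will be declared of no benefit".
- **Final analysis, enrollment already restricted.** Only the selected subgroup is tested, and the protocol refers back to options 2.1 and 2.2.

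SAP Section 2 ends the adaptive design and states that "Sections 9.2-9.4 of the prior SAP are now deleted". The deleted text included the same option 2.2. SAP 9.5 now interprets one outcome only: "Crossing of the efficacy boundary will be considered evidence that endovascular therapy is beneficial". SAP 9.6 plans a common odds ratio and a number needed to treat, each with a 95% confidence interval.

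**The concern.** Failure to reject a null hypothesis in a superiority test does not establish that null. To conclude that there is no benefit, one would need an interval that excludes every effect worth having, judged against a stated margin. Protocol 3.8 sets no such margin for the final analysis. Option 2.2 therefore commits the trial in advance to a conclusion that its test cannot give.

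The wording is also uneven. Option 2.1 confines a success to the subgroup tested. Option 2.2 names no population, so a miss in one subgroup reads as a conclusion about the therapy as a whole.

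What is at stake is the published conclusion of a trial that misses its bound although the treatment works.

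**Working it through.** **Inputs.** From Protocol 3.8: the projected mRS table, standardized effects of 0.36 (anticipated) and 0.30 (conservative), 1:1 allocation, looks at 200, 340 and 476 patients, and the powers in Table 3. From the superseded SAP 9.3: bounds of 2.62 (interim efficacy), 2.61 (final efficacy) and 1.88 (interim futility), for equally filled cells.

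**Reproducing the plan's figures.**

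1. *Fixed sample size.* The mRS table gives P(endovascular better) + ½P(tie) = 0.5953 and a tie factor of 0.9783. N = (1.96 + 1.2816)² × 0.9783 / (3 × 0.0953²) ≈ 377. The plan states 376.
2. *Fixed power at N = 476.* Power = Φ(δ√(N/4 × 3/π) − 1.96), where 3/π is the Wilcoxon efficiency for a normal shift, and √(119 × 0.955) = 10.66. At δ = 0.30: Φ(3.20 − 1.96) = 89.2% (stated 89%). The average effects in scenarios 2 and 3 give 56.8% and 42.7% (stated 55% and 41%).

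**What the label can cover at N = 476.** Effect = Z/10.66, and the 95% half-width is 1.96/10.66 = 0.184. These intervals are nominal; they ignore the interim looks and subgroup selection.

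| Overall Z | Effect | Nominal 95% CI |
|---|---|---|
| 0 | 0 | −0.18 to 0.18 |
| 1.24 | 0.12 | −0.07 to 0.30 |
| 1.96 | 0.18 | 0.00 to 0.37 |
| 2.60 | 0.24 | 0.06 to 0.43 |

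Z = 2.60 has a one-sided p of 0.0047 and misses 2.61. If the selected subgroup also misses, option 2.2 applies although the interval excludes zero and contains both 0.30 and 0.36. Only an overall Z of about 1.24 or less puts the upper limit at or below 0.30.

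**How often the label would be applied to an effective treatment.** Table 3 gives total miss rates directly: 1 − 0.80 = 20%, 1 − 0.86 = 14% and 1 − 0.87 = 13%. These include interim futility stops, which are not labelled as no benefit. To separate the two, I simulated the design with six equal nested cells, 40,000 trials per scenario. The exact futility rule is in SAP appendices that are not in the documents. I therefore assumed that 1.88 is a likelihood-ratio distance from an implied alternative, and ran four versions of that alternative.

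| True effect | Stated power | Simulated power | Interim futility stop | Final no-benefit label |
|---|---|---|---|---|
| Uniform 0.30 | 80% | 80% | 1-5% | 15-19% |
| Scenario 2 | 86% | 84-87% | 1-2% | 11-16% |
| Scenario 3 | 87% | 84-87% | 1-2% | 10-15% |
| Uniform 0.36 | not stated | 92-93% | 0-2% | 6-7% |

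Under the null, two of the versions give average sample sizes of 354 and 368 and futility stops of 66% and 60%. These bracket the stated 361 and 63%, so the assumed form is close to the plan's.

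**The case against.** The strongest reply is that the rule has lapsed. The SAP ended adaptation, removed its own copy of the sentence, attaches no such label to a miss, and already plans estimates with intervals. In addition, the protocol's next sentence speaks of declaring either efficacy or its absence, so option 2.2 may be shorthand for efficacy not declared. The label alters no test, alpha, sample size or enrollment decision. Most of this stands, and it limits the point to wording. But the SAP deletion covers only the SAP, the protocol sentence was left in place, and no current text says what a miss means.

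Three stronger readings are tempting, and the documents do not support them.

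- *Every missed bound leads to the label.* It does not. Option 2.2 belongs to the final analysis and, if enrollment stayed overall, follows a second, subgroup test.
- *The problem grows at 182 patients.* At one-sided 0.023, the mRS table gives a mean Z of 0.0953 × √(3 × 182/0.9783) = 2.25 against a critical value of 1.995, so power is about 60%. A reader might take the other 40% as the mislabelling rate. That analysis is the SAP's analysis if the trial stops, and the SAP gives it no rule for a miss. The SAP says the study may follow the current protocol only where recruitment continues; there, alpha is 0.001 and the sample size is to be reassessed. The two branches cannot be joined.
- *Misses of 45-59% occur in scenarios 2 and 3.* Those rates (1 − 0.55 and 1 − 0.41) belong to the fixed comparator design, not to the planned one.

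**Conclusion.** The point holds as a defect of wording and inference in Protocol 3.8, still unreconciled with the SAP. Option 2.2 states a conclusion that a missed superiority bound cannot support, and after a subgroup-only test it states it for the whole therapy.

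Under the adaptive design the label would fall on about 15-19% of trials at the conservative uniform effect of 0.30 and on 6-7% at the anticipated 0.36. Those two ranges rest on the assumed futility form, equal cells and the superseded bounds. The 20% total miss rate at 0.30 needs only Table 3. The Z = 2.60 example rests on the 2.61 bound, a nominal interval and a subgroup that also misses. No miss rate is claimed for the analysis of 182 patients or for continuation at 0.001.

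**What to change.** In Protocol 3.8, replace option 2.2 with: *If the efficacy bound is not crossed, efficacy has not been demonstrated in the population tested; the treatment effect estimate and its 95% CI will be reported, adjusted for the design if a subgroup was selected.* Make the later reference to options 2.1 and 2.2 point to this wording.

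Add a matching sentence to SAP 9.5 for a boundary that is not crossed, using the common odds ratio and 95% CI already planned in SAP 9.6. Do not add a check against the projected effect, because neither document states that effect as a common odds ratio.

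The cost is one sentence in each document, with no new data or patients. The current SAP path needs no new analysis. If the protocol's subgroup path were ever used, a method for the design-adjusted interval would have to be named, because SAP 9.6 no longer adjusts for the design.
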